6.7 Excluded Treatments and/or Procedures During Study Period

The following treatments are not permitted during the study:

- Prescription lipid regulating medications (eg, non-study ezetimibe, or fibrates and derivatives)
- **However, the following agents are allowed:**
 - bile-acid sequestering resin
 - stanol and stanol esters
 - **Please note: subjects on a low (lowest available recommended starting dose approved by the Japanese Ministry of Health, Labour and Welfare) or atypical dose of statins may continue their current dose if the subject has taken it for at least 4 weeks prior to the screening; new statin initiations, and/or dose adjustments are not permitted during screening or the study itself.**
- Red yeast rice, niacin > 200 mg per day
- Any other drug that significantly affects lipid metabolism (eg, systemic cyclosporine, systemic steroids [IV, IM, or PO] (*Note: hormone replacement therapy is permitted, vitamin A derivatives and retinol derivatives for the treatment of dermatologic conditions [eg, Accutane]*). Vitamin A as part of a multivitamin preparation is permitted.

- Prescribed amphetamines, or amphetamine derivatives, and weight loss medications.

Should there be a clinical need to prescribe one of these treatments, the investigator should call the Amgen Medical Monitor to discuss.

7. STUDY PROCEDURES

7.1 Schedule of Assessments

Table 1. Schedule of Assessments

Study Day / Timepoint	Screening & Placebo Run-in	D1 Visit	W2 Visit	W4	W6	W8 Visit	W10 Visit	W12 Visit	W24 Visit	W36 Visit	W48 Visit	W52 Visit	W54 ⁱ EOS Phone Call
General Procedures													
Informed consent	X												
Medical history	X												
Vital Signs (sitting BP, HR, RR, Temp)	X	X				X	X	X	X	X	X	X	
Review for AE/SAE/ADE ^a	X	X	X			X	X	X	X	X	X	X	X
Concomitant therapy	X	X	X			X	X	X	X	X	X	X	X
Dietary instruction	X	X	X			X	X	X					
Physical exam	X							X				X	
Body weight, waist circumference	X											X	
Body height	X												
SF-36		X						X					
Randomization		X											
Central Laboratory													
Fasting lipids ^b	X	X	X			X	X	X	X	X	X	X	
ApoA1, ApoB, Lp(a)		X					X	X	X	X	X	X	
PK, PCSK9		X	X				X	X				X	
Chemistry ^c Hematology ^d	X	X				X		X				X	
hsCRP		X						X				X	
HbA1c	X							X				X	
TSH	X												
Biomarkers (blood)		X						X				X	
Anti-evolocumab antibodies		X						X				X	
HCV antibodies	X												
HCV viral load (only HCV positive patients)		X						X				X	
Serum pregnancy; FSH	X							X				X	
Urine pregnancy^e		X	X			X	X	X					
Urinalysis ^f	X	X						X				X	
SC Placebo Run-in	X												
Q2W SC IP on-site		X	X			X	X	X					
Q2W SC IP non-clinic setting ^g				X	X				X	X	X		
Q2W IP Dispensation/Accountability		X	X			X	X	X	X	X	X	X	
QM SC IP on-site		X				X		X					
QM SC IP non-clinic setting ^h				X					X	X	X		
QM IP Dispensation/Accountability		X	X			X		X	X	X	X	X	
PO IP Dispensation/Accountability		X	X			X	X	X					

Footnotes defined on next page of the table

^a **Review for adverse events, serious adverse events, and adverse device effects. Adverse events possibly related to study procedures, adverse device effects, and serious adverse events** are collected **during the screening period** from signing of the ICF through 30 days post last dose of IP or EOS, whichever is later.

^b Fasting lipids: Total cholesterol, HDL-C, LDL-C, Triglycerides, VLDL-C, non-HDL-C.

^c Chemistry: Sodium, Potassium, Chloride, Bicarbonate, Total protein, Albumin, Calcium, Magnesium, Phosphorus, Fasting Glucose, BUN or Urea, Creatinine, Uric acid, Total bilirubin, Direct bilirubin, CK, Alk phos, LDH, AST (SGOT), ALT (SGPT).

^d Hematology: RBC, Hemoglobin, Hematocrit, MCV, MCH, MCHC, RDW, WBC, Platelets

^e Prior to on-site SC IP administration, **female** subjects of childbearing potential should have urine pregnancy test performed.

^f Urinalysis: Specific gravity, pH, Blood, Protein, Glucose, Bilirubin, WBC, RBC, Epithelial cells, Bacteria, Casts, Crystals.

^g Subjects on Q2W dosing will continue non-clinic setting injections after the Week 12 visit per dosing regimen.

^h Subjects on QM dosing will continue non-clinic setting injections after the Week 12 visit per dosing regimen.

ⁱ **For Q2W subjects only.**

7.2 General Study Procedures

Written informed consent must be obtained and will be implemented before protocol specific procedures are carried out. The risks and benefits of participating in the study will be verbally explained to each potential subject prior to entering into the study. The study includes collection of biomarker samples, where approved by the independent ethics committee and/or institutional review board (IEC/IRB) . If IP is administered during a study visit, administration should occur after completion of vital signs and blood draw procedures, as applicable.

Subjects must be fasting for ≥ 9 hours before each study visit where fasting laboratory samples are obtained. If the subject is not fasting for any screening visit or the Day 1 visit, no laboratory samples should be collected and the subject must return as soon as possible in a fasting state for the visit. If the subject is not fasting for any visit with evaluation of lipids after study Day 1, all visit procedures, including investigational product administration, should be completed except for the fasting lipid blood sample. Please make sure to schedule an extra visit for the fasting sample collection, if possible within the window for the respective visit.

The Analyte Listing below outlines the specific analytes for serum chemistry, hematology, urinalysis, and other testing to be conducted.

Analyte Listing

Chemistry

Sodium
Potassium
Chloride
Bicarbonate
Total protein
Albumin
Calcium
Magnesium
Phosphorus
Fasting Glucose
BUN or Urea
Creatinine
Uric acid
Total bilirubin
Direct bilirubin
CK
Alk phos
LDH
AST (SGOT)
ALT (SGPT)

Urinalysis

Specific gravity
pH
Blood
Protein
Glucose
Bilirubin
WBC
RBC
Epithelial cells
Bacteria
Casts
Crystals

Hematology

RBC
Hemoglobin
Hematocrit
MCV
MCH
MCHC
RDW
WBC
Platelets

Other Labs

Fasting lipids

- Total cholesterol
- HDL-C
- LDL-C
- Triglycerides
- VLDL-C
- non-HDL-C

ApoA1
ApoB
hsCRP
LP(a)
Anti-evolocumab antibodies
PCSK9
HbA1c
Pregnancy test (females of childbearing potential)
FSH (if needed per [exclusion 219](#))
TSH
PK & biomarkers
HCV antibody*
HCV viral load**

*HCV antibodies are measured before initiating treatment with investigational product in subjects at high risk for HCV infection and in subjects with ALT or AST > 2x ULN at any time during screening. **Conditions that may place subjects at high risk for HCV infection include the following:**

- Ever injected illegal drugs
- Received clotting factors made before 1987
- Received blood/organs before July 1992 or were exposed to blood known to be infected with HCV
- Were ever on chronic hemodialysis
- Are known to be infected with HIV
- Have a known HCV-infected sexual partner

**Viral load will be tested at the time points indicated in Schedule of Assessments, only in subjects who are positive for HCV.

Some laboratory results may inadvertently unblind investigators to treatment assignment to evolocumab. Central laboratory results of the lipid panel, ApoA1, ApoB, Lp(a), and hsCRP posttreatment to week 24 will not be reported to the investigator until the unblinding of the clinical database. Investigators should not perform non-protocol testing of these analytes during a subject's study participation from first administration of IP until at least 24 weeks after the subject's first blinded IP administration. Investigators will be informed if triglycerides are > 1000 mg/dL (11.3 mmol/L) so that appropriate subject follow-up can be initiated.

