Abbreviation or Term	Definition/Explanation
OLEAS	Open Label Extension Analysis Set
PBO	Placebo
PCI	Percutaneous coronary intervention
PCSK9	Proprotein convertase subtilisin/kexin type 9
PKPD	Pharmacokinetic / pharmacodynamics
PO	Oral administration
Q2W	Q2W is defined as every 2 weeks with a window of \pm 3 days
Q4W	Every 4 weeks, (AMG 145 Background Section)
QD	Each day
QM	QM is defined as every 4 weeks with a window of \pm 7 days
QW	Every week
Randomized	Assignment to treatment group based on computer-generated randomization schedules prepared by Amgen before the start of the study
RAS	Rechallenge Analysis Set
RBC	Red blood cells
RR	Respiratory rate
SBP	Systolic blood pressure
SC	Subcutaneous
SD	Standard deviation
SF-36	Short Form (36) Health Survey
Source Data	Information from an original record or certified a copy of the original record containing patient information for use in clinical research. The information may include, but is not limited to, clinical findings, observations, or other activities in a clinical trial necessary for the reconstruction and evaluation of the trial. Source data are contained in source documents (original records or certified copies). (ICH Guideline (E6)). Examples of source data include Subject ID, Randomization ID, and Stratification Value.
TBL	Total bilirubin
TIA	Transient ischemic attack
Tmax	Time to maximum concentration
TSH	Thyroid stimulating hormone
ULN	Upper limit of normal
VLDL-C	Very low-density lipoprotein cholesterol
WBC	White blood cell

TABLE OF CONTENTS

Protocol Synopsis	3
Study 20140234 Treatment Schema	7
Study Glossary	8
1. OBJECTIVES	15
1.1 Primary	15
1.2 Secondary	15
2. BACKGROUND AND RATIONALE	15
2.1 Disease	15
2.2 Amgen Investigational Product Background	18
2.3 Non-Amgen Medicinal Product Background	19
2.4 Rationale	20
2.5 Clinical Hypotheses	21
3. EXPERIMENTAL PLAN	21
3.1 Study Design	21
3.2 Number of Sites	22
3.3 Number of Subjects	22
3.4 Replacement of Subjects	22
3.5 Estimated Study Duration	22
3.5.1 Study Duration for Subjects	22
3.5.2 End of Study	23
4. SUBJECT ELIGIBILITY	23
4.1 Inclusion and Exclusion Criteria	23
4.1.1 Inclusion Criteria	23
4.1.2 Exclusion Criteria	24
5. SUBJECT ENROLLMENT	27
5.1 Randomization/Treatment Assignment	27
5.2 Site Personnel Access to Individual Treatment Assignments	28
6. TREATMENT PROCEDURES	28
6.1 Classification of Product(s) and/or Medical Device(s)	29
6.2 Investigational Product	29
6.2.1 Amgen Investigational Product Evolocumab (AMG 145)	29

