6.2.1.1 Dosage, Administration, and Schedule

IP will be administered SC (evolocumab or matched placebo) in accordance with instructions in the IPIM. **For visits with IP administration at the study site, administration should be the last procedure to be performed during each visit.** The date and time of evolocumab or placebo will be recorded on the individual subject's worksheet and eCRF. After **the first** IP administration at **the first** dosing visit, subjects should be observed for at least 30 minutes before being discharged.

Details of preparing and administering IP are included in the IPIM provided by Amgen at the start of the study. The dosing schedule is described by a [schema](#) in the protocol synopsis.

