- SF-36
- Central Laboratory Assessments as Per Schedule of Assessments
- **Urine pregnancy test (for female subjects of childbearing potential only): precedes on-site SC IP administration**
- PO IP tablet count
- SC IP dispensing (subjects will continue with the previously assigned dosing regimen of Q2W or QM)
- Remind patients to discontinue blinded oral IP
- SC IP administration on-site (all subjects)

7.2.3.8 Visit/Week 24

The following procedures will need to be conducted at this visit for all subjects unless specified otherwise (± 3 days).

- Vital signs (eg, sitting blood pressure, heart rate, respiratory rate, temperature)
- Review for **adverse events**, **serious adverse events**, **and adverse device effects**
- Documentation of concomitant medications
- Central Laboratory Assessments as Per Schedule of Assessments
- SC IP dispensing (subjects will continue with the previously assigned dosing regimen of Q2W or QM)

7.2.3.9 Visit/Week 36

The following procedures will need to be conducted at this visit for all subjects unless specified otherwise (± 3 days).

- Vital signs (eg, sitting blood pressure, heart rate, respiratory rate, temperature)
- Review for **adverse events**, **serious adverse events**, **and adverse device effects**
- Documentation of concomitant medications
- Central Laboratory Assessments as Per Schedule of Assessments
- SC IP dispensing (subjects will continue with the previously assigned dosing regimen of Q2W or QM)

7.2.3.10 Visit/Week 48

The following procedures will need to be conducted at this visit for all subjects unless specified otherwise (± 3 days).

- Vital signs (eg, sitting blood pressure, heart rate, respiratory rate, temperature)
- Review for **adverse events**, **serious adverse events**, **and adverse device effects**
- Documentation of concomitant medications
- Central Laboratory Assessments as Per Schedule of Assessments
- SC IP dispensing (subjects will continue with the previously assigned dosing regimen of Q2W or QM)

7.2.3.11 Visit/Week 52

The following procedures will need to be conducted at this visit for all subjects unless specified otherwise (± 3 days).

- Vital signs (eg, sitting blood pressure, heart rate, respiratory rate, temperature)
- Review for **adverse events**, **serious adverse events**, **and adverse device effects**
- Documentation of concomitant medications
- Physical exam

- Body weight and waist circumference
- Central Laboratory Assessments as Per Schedule of Assessments

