10.4.2 Primary Analysis

To evaluate efficacy and safety of 12 weeks of evolocumab compared with ezetimibe **and summarize 12 weeks of data from the open-label extension (weeks 12 to 24)**, the primary analysis will be performed when all the randomized subjects in the study have either completed the scheduled visits up to and including Week **24** or have early terminated from the study. At that time, the database of the study will be cleaned, processed and a snapshot will be taken; the study will also be unblinded.

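### A non-fasting subject at Week 12 is dosed before the make-up lipid draw, so the Week 12 LDL-C is probably lost or taken after open-label evolocumab: a small effect, cheaply avoided

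*Protocol*

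**What the plan says.** **Protocol.** Section 7.2 treats non-fasting subjects in two ways. At screening or Day 1 no sample is taken and the subject returns fasting. At any later lipid visit, "all visit procedures, including investigational product administration, should be completed except for the fasting lipid blood sample", with an extra visit for the sample, "if possible within the window for the respective visit". Elsewhere the order is the reverse: Section 6.2.1.1 says of on-site dosing that "administration should be the last procedure to be performed during each visit".

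At Week 12 (Day 85 ± 3, Section 7.2.3.7) all subjects receive SC IP on site, and the site is told: "Remind patients to discontinue blinded oral IP". Section 3.1 ends oral IP with the Week 12 visit and has open-label evolocumab follow. Section 10.4.2 describes weeks 12 to 24 as 12 weeks of open-label data.

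**SAP.** Section 6.3 assigns measurements to study weeks by the Appendix B windows. For fasting lipids the Week 12 window is (77, min(91, first OLE dose day)]. The Week 24 window opens immediately afterwards, and the record nearest Day 169 is used. Appendix B introduces its windows for descriptive summaries; Section 6.3 states them without that limit.

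Missing lipids are not imputed in the repeated measures model (Section 10.5.1.1). A missing Week 12 LDL-C counts as not reaching < 70 mg/dL (Section 6.3). The completer set requires observed co-primary values (Section 7.2). Each Tier 1 pair is judged on its larger p-value (Table 3).

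**The concern.** Each rule is sensible alone. Together they mean that a site following Section 7.2 exactly at Week 12 can turn a recoverable value into a missing one. The make-up draw meets the protocol's visit window, yet the dose just given has already closed the SAP's window.

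What is at stake is the Week 12 half of the co-primary pair, and the same half of 5 of 7 Tier 1 pairs (LDL-C change, LDL-C response, total cholesterol, non-HDL-C, total cholesterol/HDL-C) and 3 of 4 Tier 2 pairs (triglycerides, HDL-C, VLDL-C). ApoA1, ApoB and Lp(a) stand on a separate row of Table 1, so the text does not defer them.

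**Working it through.** **1. Is the Week 12 injection the first open-label dose?** Sections 3.1, 7.2.3.7 and 10.4.2 point that way. The SAP window gives a further test. Were the Week 12 injection still blinded, the first open-label dose would fall as follows:
- Q2W: 85 + 14 = Day 99, earliest 82 + 11 = Day 93.
- QM: 85 + 28 = Day 113, earliest 82 + 21 = Day 103.

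All exceed 91, so the open-label term in min(91, first OLE dose day) would never apply on schedule. The inference is strong, but nothing states it outright.

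**2. Where does the make-up draw go?** With dosing on Day 85 the window is (77, 85]. A later draw the same day still counts. Draws on Days 86–88, inside the protocol's Days 82–88, become Week 24 records. They lie 169 − 86 = 83 to 169 − 88 = 81 days from Day 169, so a real Week 24 sample displaces them.

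**3. The plan's own power.** Protocol Section 10.2 gives 40 vs 20 subjects, 5% receiving no IP (38 vs 19), difference 20, SD 20, two-sided 0.05. SE = 20·√(1/38 + 1/19) = 5.62; noncentrality 20/5.62 = 3.56; power 93.8%. This agrees with the stated figure of at least 93%.

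**4. Week 12 co-primary with values lost.** Assumptions: four visits (Weeks 2, 8, 10, 12), equal correlation ρ of 0.5 to 0.8 (not in the documents), 54 df. With m of n subjects lacking only Week 12, the variance of an arm's Week 12 mean is

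20²·[(1 − R²)/(n − m) + R²/n], with R² = 3ρ²/(1 + 2ρ), that is 0.375 at ρ = 0.5 and 0.738 at ρ = 0.8.

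Example, 2 evolocumab and 1 ezetimibe lost, ρ = 0.5: 0.625/36 + 0.375/38 + 0.625/18 + 0.375/19 = 0.0817; SE = 20·√0.0817 = 5.72; noncentrality 3.50; power 93.0%.

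| Lost (evolocumab, ezetimibe) | ρ = 0.5 | ρ = 0.8 |
|---|---|---|
| 0, 0 | 93.8% | 93.8% |
| 1, 0 | 93.6% | 93.7% |
| 0, 1 | 93.3% | 93.6% |
| 2, 1 | 93.0% | 93.4% |

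At 36.9 points, the smaller of the two effects that Section 10.2 cites from the earlier global study, power stays above 99.99% in every row.

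**5. Week 12 LDL-C response.** The model cannot help here, because a lost value is scored as failure. Each lost evolocumab responder lowers that arm's rate by 1/38 = 2.6 points. The check is an exact binomial enumeration of an unstratified 1-df chi-square with the N − 1 factor, 38 vs 19, at 0.005 (the Hochberg threshold if response has the largest of the seven Tier 1 p-values). The response rates are assumptions.

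| Assumed rates | None lost | 1 evolocumab lost |
|---|---|---|
| 40% vs 2% | 68.2% | 64.2% |
| 50% vs 2% | 92.9% | 91.2% |
| 60% vs 2% | 99.2% | 98.9% |

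One lost ezetimibe subject works the other way: at 50% vs 2%, power moves from 92.9% to 93.3%. Response for the Week 10/12 mean uses the available Week 10 value, so only the Week 12 half of the pair is hit.

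**The case against.** The best defence is that the data loss depends on two readings that the documents do not settle. The Week 12 injection is not named as the first open-label dose, and the dosing schema is not shown. If that injection were blinded, the window would run to Day 91 and draws on Days 86–88 would count. The SAP's cap on blinded SC exposure does not settle this, because it counts from the last blinded dose, whichever that was. Appendix B may also not govern the model; under nominal visits no value is lost. Both points stand as conditions. The second does not clear the plan, because the nominal reading admits a value drawn after open-label evolocumab.

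It is also fair that dosing on schedule is defensible, that Section 7.2 already requires at least 9 hours' fasting before such visits, and that the SAP cut-off rightly keeps post-open-label draws out of the comparison with ezetimibe. These points limit the importance of the matter.

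Two stronger readings are tempting. A reader might infer that the trial's power is threatened; the table under step 4 shows otherwise. A reader might also take the lowest Hochberg threshold, 0.005/7, and find a larger loss in response power. That threshold decides only if response has the smallest Tier 1 p-value and every other pair misses its own threshold. This is implausible beside LDL-C change, given the cited effects of 36.9 and 37.6 points.

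**Conclusion.** A minor point that holds conditionally. If the Week 12 injection starts the open-label period, a later-day make-up draw either drops out of Week 12 or counts there after open-label evolocumab. Neither result is wanted, and the cause is the order in Section 7.2, not the SAP window.

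Under the Appendix B reading the cost is at most about half a percentage point of Week 12 co-primary power per lost subject at a 20-point effect. For Week 12 response at 0.005, one lost evolocumab subject costs 0.3 to 4.0 points over the assumed rates in step 5. If the response pair failed for this reason, Tier 2 would be tested at 0.045 instead of 0.05. No size is claimed for the nominal-visit reading. How often any of this happens is unknown, because no non-fasting rate is given.

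**What to change.** In Section 7.2 add, for Week 12 only:

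> If the subject is not fasting at Week 12, hold SC IP and continue blinded oral IP until the fasting lipid sample is drawn within the ±3-day visit window (no later than Day 88), then give SC IP the same day. If no fasting sample is obtained by Day 88, give SC IP and stop oral IP that day.

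In Section 7.2.3.7, move the SC dose, the urine pregnancy test that precedes it and the reminder to stop oral IP to the make-up visit, and check that oral supply covers the delay.

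The SAP needs no change: a draw on the day of the held dose lies inside (77, min(91, first OLE dose day)]. The Day 88 limit keeps dosing within the visit window, as Section 6.2.1.2 asks. From an on-schedule previous dose, Q2W runs 88 − 71 = 17 days (limit 14 + 3 = 17) and QM runs 88 − 57 = 31 days (limit 28 + 7 = 35).

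Costs:
- The dose is delayed by a few days at most, and the Week 12 LDL-C is measured slightly later after the last evolocumab dose. Any waning would count against evolocumab, since oral treatment continues daily.
- Oral IP may run from Day 71 to Day 87 (17 doses) instead of to Day 84 (14 doses). Pack size is not given.
- A subject who first attends non-fasting on Day 88 is not rescued.
- The extra visit is no new cost, because the current rule already requires it.

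For this trial the text comes too late: SAP Section 10.1 records the primary analysis as complete and says the blinded-period analyses will not be repeated. What remains is one count in the CSR, by arm: Week 12 fasting lipid samples drawn after the first open-label dose. The missing-data summaries in SAP Section 9.3.1 show how many values are missing but do not commit to reporting this cause.

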7.2.1 Placebo Run-in

In order to reduce the burden of unnecessary procedures on subjects who subsequently elect not to participate in the study or continue with study procedures, all subjects will enter a placebo run-in period to confirm tolerance of SC administration prior to randomization. This placebo run-in period can be started before or after venipuncture procedures for the study and will consist of SC administration of placebo consisting of the AI/Pen. This administration will follow the same procedures as injections of IP using the AI/Pen during the treatment period. Further details will be provided in the IPIM.

7.2.2 Screening Enrollment and/or Randomization

The following procedures are to be completed during the screening period of subjects at time points designated in the Schedule of Assessments:

- Informed Consent Form signed
- Medical history
- Vital signs (eg, sitting blood pressure, heart rate, respiratory rate, temperature)
- Review for **adverse events, serious adverse events, and adverse device effects**. **Adverse events** possibly related to study procedures, **adverse device effects**, and **serious adverse events** are collected during the screening period from signing of the ICF
- Documentation of concomitant medications
- Dietary instruction: subject will be counseled on the importance of maintaining a "heart-healthy" diet throughout the course of the study; medication compliance reminder
- Physical exam
- Body height
- Body weight and waist circumference
- Central Laboratory Assessments (**as per Schedule of Assessments**):
 - Blood draw for fasting lipids (≥ 9 hour fasting sample), chemistry (including fasting glucose), CK, hematology, HbA1c, TSH, (Note: eGFR will be calculated by the central laboratory and will be provided to the site for eligibility)

determination), blood draws for hepatitis C virus (HCV) antibodies in subjects at high risk for, or with history of, HCV infection and in subjects with AST or ALT > 2x ULN at any time during screening, serum FSH (only if required to ensure menopause in a female subject by central laboratory)

- Serum pregnancy (females of childbearing potential only)
- Urine sample for urinalysis
- **Subject instruction on self-administration of evolocumab for AI/Pen or Personal Injector**
- AI/Pen placebo injection (does not need to be repeated for rescreening)

